
	
The purpose of this study is to test if remote limb ischemic conditioning will enhance motor learning in neurologically intact middle-aged and older adults who are of a similar age and present with similar comorbidities as persons with stroke. . We previously found that combining behavioral training and RLIC facilitated motor learning in healthy young adults under 40.¹⁰The primary aim of this study is to determine if training + RLIC facilitates the learning of motor tasks in an older population beyond the healthy young population that we have previously tested.
																
Study Design	Between subjects repeated measures design. Please refer to Figure 1.																
Groups	
Group 1: Neurologically Intact Subjects + RLIC conditioning Group 2: Neurologically Intact Subjects + sham conditioning
 
Subjects who qualify and consent will be randomly assigned to either group 1 or 2.. Allocation will be concealed from those responsible for assessing subjects for eligibility and entry into the study (e.g. sequentially numbered, opaque, sealed envelopes).
																

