Number of Subjects & Power Analysis	
Based off of our pilot data on the balance training task we need the following total sample sizes moving forward (see Table 1 below) to achieve at least 80% power to detect the mean differences of change scores (posttest – pretest) between the two treatment groups (RLIC vs. sham) based on a two-sample t-test at a significance level of 0.05. The standard deviations for change scores are assumed to be 2.5 seconds and 1.9 seconds for the RLIC and sham groups, respectively. Moving forward, we will recruit 10 subjects per group (n=40). This will give us the ability to detect differences on the balance task of at least 3 seconds or more. Differences less than 3 seconds (and smaller effect sizes) are unlikely to be clinically-relevant in future target populations. We continue to request permission to enroll 130 subjects total 51 of whom have already been enrolled) to allow for screen failures and participants who do not complete all study visits.
 
Table 1. Power analysis
 
  
 Mean difference of change score	Total sample size (assume equal sample size in each group)	
   
 7 seconds	12 (with actual power 93%)	
 
 6	12 (with actual power 85%)	
 
 5	15	
 
 4	21	
 
 3	30	
 
 2	63	
 
 1	237	
  
	Mean difference of change score	Total sample size (assume equal sample size in each group)	7 seconds	12 (with actual power 93%)	6	12 (with actual power 85%)	5	15	4	21	3	30	2	63	1	237
Mean difference of change score	Total sample size (assume equal sample size in each group)																
7 seconds	12 (with actual power 93%)																
6	12 (with actual power 85%)																
5	15																
4	21																
3	30																
2	63																
1	237																

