Behavioral Training Parameters	
Participants will receive behavioral training on D3-D7 on a balance training task (15 minutes; rest breaks as needed)
 
The balance training task is a lower extremity standing balance task.¹¹ The balance task requires subjects to stand on a movable platform (stability platform, model 16030L, Lafayette Instrument) and to keep the platform in a balanced, horizontal position.¹¹ This is a lab-based test. This motor task was selected because it simulates the balance required for

	daily function, and can be easily modified to the appropriate level of difficulty in accordance with each subject's motor abilities.
Descriptive measures	Demographic information, including age, dominant side, gender, ethnicity, race, level of physical activity, first day of last menstrual cycle, height, body weight, employment status, education level, living status, co-morbidities, and current medications will be collected on all subjects during D1.
Primary Outcome Measures	
The outcome measure is change in balance score on the balance task.
 
Performance on the balance task will be quantified by identifying the number of seconds in a 30-second trial that an individual is able to maintain the platform within $\pm 3^\circ$ of horizontal. 5 trials are averaged for the baseline, after the intervention, and at follow-ups.
 
Balance change scores will be computed as the difference from the end of intervention minus the baseline (in seconds).

Data Analysis	
Data will be analyzed using a mixed model analyses examining group differences and interactions between group and various subject characteristics.
 
Our first hypothesis is that both the RLIC and sham groups will demonstrate improved performance on the balance task and arm task, with practice (main effect of time). Secondly, we hypothesize that RLIC will facilitate motor learning to a greater extent than the sham group, so that subjects given RLIC will demonstrate greater improvements in performance on the balance task and arm task than individuals given sham treatment (group x time interaction).
 
Additional analyses are planned per the funded project and include explorations into how various subject characteristics influence/interact with the RLIC vs. sham conditioning. These factors include age, sex, BMI, and the presence/absence of cardiovascular comorbidities and medications.

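### Ten per group in a two-group trial is 20, not 40, and Table 1's two-group totals are three times, not twice, the number needed per group

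*Combined protocol and SAP*

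**What the plan says.** The protocol's Groups section lists RLIC and sham and states: "Subjects who qualify and consent will be randomly assigned to either group 1 or 2". Item 1.3 of the IRB form also describes two randomised groups.

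The section Number of Subjects & Power Analysis aims for at least 80% power on change scores, "between the two treatment groups (RLIC vs. sham) based on a two-sample t-test at a significance level of 0.05", with SDs of 2.5 s (RLIC) and 1.9 s (sham). It then says "Moving forward, we will recruit 10 subjects per group (n=40" in parentheses, and that this size can detect 3 s or more. On smaller effects it says: "Differences less than 3 seconds (and smaller effect sizes) are unlikely to be clinically-relevant in future target populations".

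Table 1 heads its column "Total sample size (assume equal sample size in each group" and prints 12, 12, 15, 21, 30, 63 and 237 for differences of 7, 6, 5, 4, 3, 2 and 1 s. The 7 s entry reads "12 (with actual power 93" percent, and the 6 s entry gives 85% for the same total.

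On enrolment the section says: "We continue to request permission to enroll 130 subjects total 51 of whom have already been enrolled". The allowance is for screen failures and non-completers. Under Data Analysis the plan is: "Data will be analyzed using a mixed model analyses examining group differences and interactions between group and various subject characteristics".

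**The concern.** The same section implies three totals for the same 3 s target: 20 (10 in each of two groups), 30 (Table 1) and 40 (the parenthesis). The recruitment target decides when enrolment ends and how many people undergo repeated cuff conditioning. With the target ambiguous, the stopping point is open to choice, while item 1.19 of the IRB form has the investigators reviewing accrued data weekly.

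Table 1 also looks wrong on its face. Four of its totals (15, 21, 63, 237) are odd and cannot be split into two equal groups. Anyone using it to size the trial for another effect would recruit more than the stated power needs.

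**Working it through.** **Inputs.** From Number of Subjects & Power Analysis: SDs 2.5 and 1.9 s, significance level 0.05, power at least 80%, two equal groups, and the seven differences in Table 1. Assumed: a two-sided test, and the unequal-variance (Welch) form, because the SDs differ.

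**Planned size.** 2 groups × 10 = 20. To reach 40 takes 20 per group or four groups. Places left under the ceiling are 130 − 51 = 79, which accommodates 20, 30 or 40 and so does not settle the matter.

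**Method.** With n per group, the standard error of the difference is √((2.5² + 1.9²)/n) = √(9.86/n). For n = 10 this is 0.993 s, so a 3 s difference is 3/0.993 = 3.02 standard errors. For n = 20 it is 0.702 s, so 3 s is 4.27 standard errors. Power is the probability that the Welch statistic exceeds its critical value, integrated over both sample variances and checked by simulation (400,000 replicates). Exact calculation matters for the small sizes: a noncentral t with fixed Satterthwaite degrees of freedom gives 95.2% at 7 s with 4 per group, where simulation gives about 93%.

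**Reproducing Table 1.** Smallest n per group reaching 80%:

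| Difference (s) | n per group | Power at n | Power at n − 1 | 2n | 3n | Table 1 total |
|---|---|---|---|---|---|---|
| 7 | 4 | 93.1% | 71.1% | 8 | 12 | 12 |
| 6 | 4 | 84.5% | 58.7% | 8 | 12 | 12 |
| 5 | 5 | 85.1% | 70.3% | 10 | 15 | 15 |
| 4 | 7 | 85.9% | 78.3% | 14 | 21 | 21 |
| 3 | 10 | 80.8% | 75.8% | 20 | 30 | 30 |
| 2 | 21 | 81.1% | 79.0% | 42 | 63 | 63 |
| 1 | 79 | 80.3% | 79.8% | 158 | 237 | 237 |

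All seven printed totals equal 3n; none equals 2n. The printed powers of 93% and 85% belong to 4 per group. A true two-group total of 12 (6 per group) would give 99.7% and 98.3%.

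Read as two-group totals, the printed sizes give about 99.7%, 98.3%, 97.2%, 97.0%, 94.5%, 93.9% and 93.2% power for 7 down to 1 s. For the odd totals 15 and 21 these figures put the smaller group on RLIC; the other split gives 98.0% and 97.5%.

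**Sensitivity to the test.** A pooled-variance t-test needs 3, 4, 5, 6, 10, 21 and 79 per group, or 6, 8, 10, 12, 20, 42 and 158 in total. The factor of three then fits five of seven rows, and 4 per group gives about 95.6% at 7 s and 88.5% at 6 s, not the printed 93% and 85%. No printed total is the two-group requirement under this test either. A one-sided test, 90% power, and levels of 0.025, 0.0167 and 0.01 also fail to reproduce the table as two-group totals.

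**What each planned size delivers (Welch, new subjects only).**

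| Total | Per group | Power at 3 s | Difference with 80% power |
|---|---|---|---|
| 20 | 10 | 80.8% | 2.97 s |
| 40 | 20 | 98.6% | 2.02 s |

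If all 51 already enrolled were analysed too (assumption: all complete, near-equal split), the totals would be 20 + 51 = 71 or 40 + 51 = 91, detecting about 1.5 s or 1.3 s. This is an extreme case, since some of the 51 may be screen failures or non-completers.

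**The case against.** The strongest reply is that nothing is underpowered. Ten per group is the right number for 3 s, the Table 1 totals err on the large side, and the protocol itself chose 10 per group, so the fault is one of wording. That is true as to power, but it does not say whether 20 or 40 people are to be recruited.

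A second reply is that 40 may be deliberate. The Data Analysis section plans interactions of group with age, sex, BMI, and cardiovascular comorbidities and medications, and a size above the bare t-test minimum would be reasonable for those. This is possible, but the sample size section gives only the 3 s rationale and does not link 40 to anything else.

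A third is that the protocol names neither Welch nor the number of sides, so the factor of three is an inference. This stands in part: the exact match on all seven rows depends on Welch, which the two printed powers support. The finding that the totals are wrong does not depend on it, because they fail under the pooled test too, and odd totals cannot be two equal groups under any test.

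**Conclusion.** The concern holds, and the section is wrong as written. The recruitment size is stated in two ways that differ by a factor of two, and every Table 1 total is 50% above the two-group requirement under Welch. The 3 s claim for 10 per group is correct. At 40 the trial would detect about 2 s, below what the protocol treats as likely to matter clinically, so its stated rationale leads to 20 and leaves 40 unexplained. The final analysed number cannot be worked out either, because the section does not say whether the 51 already enrolled are included.

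These figures rest on the protocol's SDs and an assumed two-sided test. They approximate the power of the planned mixed model, which is not the test used for sizing. The documents do not state why the factor is three.

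**What to change.** State one intended size: either 10 per group, 20 in total, with about 81% power for 3 s; or 20 per group, 40 in total, with about 98.6% power for 3 s and 80% power for about 2.0 s. If 40 is meant, give the reason for sizing below 3 s. Say whether the number excludes the 51 already enrolled and how many of them, if any, enter the analysis.

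Name the test and its sidedness, and replace the Table 1 totals. For a two-sided Welch test they are 8 (93%), 8 (about 85%), 10, 14, 20, 42 and 158 for 7 down to 1 s; if a pooled test is intended, the 7 s and 4 s rows become 6 and 12.

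As housekeeping, reconcile the ceiling of 130 in this section with the 143 in item 2.1.a of the IRB form.

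The cost is a correction to one paragraph and one table. The correction adds no subjects; choosing between the two sizes is the investigators' decision and involves a difference of 20 subjects.

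### The first hypothesis claims improvement in each group, but its stated test, the main effect of time, conventionally tests only the average of the two groups' changes

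*Combined protocol and SAP*

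**What the plan says.** The Data Analysis section of the protocol states two hypotheses and names a test for each.

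- Hypothesis 1: "both the RLIC and sham groups will demonstrate improved performance on the balance task and arm task, with practice (main effect of time").
- Hypothesis 2: participants given RLIC will "demonstrate greater improvements in performance on the balance task and arm task than individuals given sham treatment (group x time interaction").

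The model is described in one sentence: "Data will be analyzed using a mixed model analyses examining group differences and interactions between group and various subject characteristics". The section does not say how group is coded or which time points enter the model. It plans no within-arm contrast, and it gives no rule for reading the time effect when the interaction is present.

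Under Primary Outcome Measures, "Balance change scores will be computed as the difference from the end of intervention minus the baseline (in seconds"). Under Number of Subjects & Power Analysis, the sample size is set "to achieve at least 80% power to detect the mean differences of change scores" between RLIC and sham, "based on a two-sample t-test at a significance level of 0.05". There, "The standard deviations for change scores are assumed to be 2.5 seconds and 1.9 seconds for the RLIC and sham groups, respectively".

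**The concern.** Hypothesis 1 is a conjunction: RLIC improves and sham improves. In a group-by-time model with the usual coding, the main effect of time asks whether the mean of the two arm changes differs from zero. A large change in one arm is enough to reject. Hypothesis 2 predicts that the arms change by different amounts, and if so the average describes neither arm.

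At stake is the statement that practice alone improves performance in this older population. Followed literally, the plan would let that statement be made for both groups on evidence supplied by the RLIC arm.

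**Working it through.** **Inputs.** SD of change 2.5 s (RLIC) and 1.9 s (sham), significance level 0.05 and a target difference of 3 s, all from Number of Subjects & Power Analysis. That section does not say whether the test is one- or two-sided; two-sided is assumed. It gives 10 per group beside a total of 40, which for two groups would be 20 each, so both sizes are shown. The outcome is the two-point change score. The documents give no expected sham gain, so it is varied. They give SDs for the balance task only, so nothing is computed for the arm task that the hypotheses also name.

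**1. The plan's own figure.** For 10 per group and a 3 s difference, SE = √(2.5²/10 + 1.9²/10) = √0.986 = 0.993 s and the noncentrality is 3/0.993 = 3.02. A two-sample t-test on 18 df has power 81.5% (Welch 81.2%). The stated power of at least 80% for 3 s at 10 per group is reproduced.

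**2. What the time effect tests.** With equal arms, write R and S for the mean changes in RLIC and sham.

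- Interaction: t = (R − S)/SE.
- Main effect of time: t = [(R + S)/2]/(SE/2) = (R + S)/SE.

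Both use the same SE and 2n − 2 df. When S = 0 the two statistics are identical, so the time effect adds no evidence about sham.

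**3. Chance that the time effect is significant when sham does not gain.** The SE of the averaged change is 0.5 × √(2.5²/n + 1.9²/n), which is 0.496 s at n = 10 and 0.351 s at n = 20. Noncentral t with 2n − 2 df gives:

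| True RLIC gain | True sham gain | 10 per arm | 20 per arm |
|---|---|---|---|
| 3 s | 0 s | 81.5% | 98.6% |
| 2 s | 0 s | 48% | 79% |
| 3 s | −1 s | 48% | 79% |

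The last two rows agree because (2 + 0)/2 and (3 − 1)/2 are both 1 s. Simulation of 200,000 trials agrees for the first and third rows.

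**4. Requiring each arm to improve.** Each arm's change is tested by its own one-sample t on n − 1 df, and both must be significant in the improving direction. The arms are independent, so the probabilities multiply. With RLIC +3 s and sham 0 s at 10 per arm, 0.920 × 0.025 = 2.3%; at 20 per arm, 0.999 × 0.025 = 2.5%.

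**5. Power of that rule when both arms do gain.** RLIC is set 3 s above sham:

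| Sham gain | 10 per arm | 20 per arm |
|---|---|---|
| 1 s | 32% | 61% |
| 2 s | 84% | 99% |
| 3 s | 99% | over 99% |

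The averaged time effect is significant in over 99% of trials in every row.

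**6. Variances.** At 10 per arm, a pooled SD gives nominal 95% intervals with about 92% coverage for RLIC and 97.5% for sham. Arm-specific variances avoid this and match the planning assumption of unequal SDs.

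**The case against.** **Hypothesis 1 is only a check that practice works.** This stands. The primary aim, the primary outcome and the power analysis all concern the between-group comparison. A reader might infer that RLIC cannot be said to facilitate learning unless sham improves, or that the two tests undermine each other. The documents do not support that. Arms are randomised and trained alike, so the difference in change estimates the RLIC effect whether sham gains 0 s or 3 s, and the interaction supports hypothesis 2 by itself.

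**Zero sham gain is unlikely.** Both arms receive the same 15-minute balance training on D3 to D7, so zero gain is a limiting case. A reader might infer from 81.5% that a false statement about both groups is the usual outcome. That holds only if sham truly gains nothing and RLIC gains about 3 s; with a 2 s RLIC gain it is 48% at 10 per arm. Still, hypothesis 1 exists to test the sham gain, not to assume it.

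**The computed test may not be the planned one.** The Figure 1 legend lists measurements at baseline, on the training days and at each follow-up. If all of these enter the model, the time effect has several degrees of freedom, and its rejection rate was not computed here. The percentages belong to the two-point change score. The mismatch does not depend on them: a multi-point time effect still averages the arms under the usual coding. With sham as the reference level, the time term concerns sham alone and says nothing about RLIC.

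**Requiring both arms costs power.** This also stands. If both arms truly gain 2 s, the rule succeeds in 52% of trials at 10 per arm, against 97% for the averaged effect.

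**Conclusion.** The concern holds, as a minor one. The stated test does not match the stated claim: hypothesis 1 is about each arm, and the main effect of time is, by convention, about their average. In the limiting case of RLIC +3 s and sham 0 s, the plan would support the claim about both groups in 81.5% of trials at 10 per arm and 98.6% at 20, against 2.3% to 2.5% if each arm must show its own improvement. These figures assume two time points, the protocol's SDs, equal arms, normal changes and two-sided 0.05. Only the practice claim is affected.

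**What to change.** In Data Analysis, replace the bracketed test for hypothesis 1 with wording such as: *The change from baseline to end of intervention will be estimated in each group from the same mixed model, with group-specific variances, and reported with its 95% confidence interval. Both groups will be said to have improved only if both intervals lie above zero. The time effect averaged over groups will be descriptive.*

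No multiplicity adjustment is needed, because both conditions must be met. The interaction test for hypothesis 2 stays as it is.

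The change costs one sentence and no new data. It is not free in power: for small sham gains the statement about both groups will often not be reached (step 5 of the working). That reflects real uncertainty about the sham arm which the averaged test hides, and the reported intervals will show it.
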